486 study. It reveals that our targeted VLPFC is one of the regions receiving the most intense
487 stimulation, along with the dorsal medial PFC and a portion of the DLPFC.

488

489 7. Assessments

490 7.1 Enrollment Visit

491 At the enrollment visit, consent was obtained from participants, and demographic
492 information was also collected. Paranoia screening and diagnostic interviews were performed to
493 determine eligibility. Current medications were reported by the patients, and they were asked to

494 remain on a stable dose of medication throughout their participation in the study unless
495 specifically recommended by their physician. After that, participants completed daily EMA
496 surveys for 7 days to assess baseline paranoia level and social functioning in daily life. They then
497 attended the first stimulation visit. At both stimulation visits, the Positive and Negative
498 Syndrome Scale (PANSS) (Kay et al., 1987) was administered by trained research personnel to
499 assess the full range of symptoms in individuals with SSD. Daily EMA surveys between
500 Stimulation Visit 1 and 2, as well as after Stimulation Visit 2, were also sent to participants to
501 monitor any changes in paranoia and social functioning after tDCS in the participant's day-to-
502 day life.

503 *7.2 Stimulation Visits: Pre-stimulation Assessments*

504 **Trait Paranoia.** The Paranoia Scale (PS) (Fenigstein & Venable, 1992) is a self-report
505 measure to assess trait paranoia. This measure contains 20 items (e.g., "Someone has it in for
506 me", "It is safer to trust no one") and is measured on a five-point Likert scale (1 = not at all
507 applicable, 5 = extremely applicable). Scores range from 20-100, with higher scores indicating
508 higher paranoia. The PS demonstrated good reliability and validity in previous work on patients
509 with schizophrenia (Pinkham et al., 2012; Tiernan et al., 2014). In the current study, PS showed
510 excellent internal consistency in both Stimulation Visit 1 (Cronbach's $\alpha = 0.941$) and Stimulation
511 Visit 2 (Cronbach's $\alpha = 0.930$).

512 **State Paranoia.** The State Social Paranoia Scale (SSPS) (Freeman et al., 2007) was used
513 to examine paranoia levels immediately before and at the conclusion of stimulation within each
514 visit. Participants indicated how much they agreed with each of 20 statements (e.g., "Someone
515 was hostile towards me", "Someone was trying to isolate me") using a five-point Likert scale (1

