540 have been generally linked to psychotic symptoms and paranoia but that were not of primary
541 importance and therefore not reported here. Relationships among paranoia, social decision-
542 making, and aggression were also explored in this segment for secondary analyses. Since these
543 analyses were not the main focus of the project, they are not included in the main text (details of
544 all measures administered between stimulation sessions can be found in **Appendix A**).

545 Participants were offered a 30-minute break before the second stimulation session of that visit.
546 The only measure relevant to the main goal of this study is overall social functioning as detailed
547 below:

548 ***Birchwood Social Functioning Scale (SFS; Stimulation Visit 1 and 2).*** The SFS
549 (Birchwood et al., 1990) measures 7 domains of social adjustment based on self-reports (range =
550 0-223, Cronbach's $\alpha_{\text{visit 1}} = 0.915$, Cronbach's $\alpha_{\text{visit 2}} = 0.897$), including social
551 engagement/withdrawal (range = 0-15; Cronbach's $\alpha_{\text{visit 1}} = 0.422$, Cronbach's $\alpha_{\text{visit 2}} = 0.561$),
552 interpersonal communication (range = 0-9; Cronbach's $\alpha_{\text{visit 1}} = 0.426$, Cronbach's $\alpha_{\text{visit 2}} = 0.269$),
553 prosocial activities (range = 0-66; Cronbach's $\alpha_{\text{visit 1}} = 0.879$, Cronbach's $\alpha_{\text{visit 2}} = 0.815$),
554 recreation activities (range = 0-45; Cronbach's $\alpha_{\text{visit 1}} = 0.684$, Cronbach's $\alpha_{\text{visit 2}} = 0.749$),
555 independence-competence (range = 0-39; Cronbach's $\alpha_{\text{visit 1}} = 0.911$, Cronbach's $\alpha_{\text{visit 2}} = 0.934$),
556 independence-performance (range = 0-39; Cronbach's $\alpha_{\text{visit 1}} = 0.915$, Cronbach's $\alpha_{\text{visit 2}} = 0.920$),
557 and employment (single item; range = 0-10). A higher score on each subscale indicates better
558 functioning in the respective social domain, while a higher overall score signifies better social
559 functioning in general. The SFS was originally developed for schizophrenia patients and has
560 been widely used to measure social functioning outcomes in this population (Birchwood et al.,
561 1990; Burns & Patrick, 2007).

562 *6.7 Stimulation Visits: Post-stimulation Assessments*

563 ***State Paranoia and State Anxiety.*** SSPS and STAI-S were administered as described in
564 the pre-stimulation assessments.

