618 along a 7-point scale, as well as the emotions associated with and perceptions of social
619 interactions since the last survey (e.g., did you interact with anyone since your last survey?).
620 Affective states since the past alarm were rated on a 7-point scale using the following items:
621 sad/depressed, excited, irritated, happy, belongingness, and burden to others. Expectations

622 regarding subsequent interpersonal situations were also rated on a 7-point scale (e.g., how much
623 interest do you have in interacting with people for the rest of the day?). **Appendix B** contains the
624 complete list of EMA questions (i.e., paranoia: Q1; social functioning: Q3, Q4, Q5, Q6, Q7, Q14,
625 Q15). Adherence was monitored remotely via a secure platform, and participants who missed 3
626 consecutive surveys were contacted by research personnel to identify and resolve any issues.
627 Compensation of the EMA periods was determined by the actual number of surveys completed
628 to encourage adherence.

629 A total of 47 (out of 50) participants had full data across three EMA periods. One
630 participant did not have a phone and chose not to participate in the EMA protocol. Two
631 participants completed baseline EMA but lost their phones afterwards, and thus chose not to
632 complete the two remaining EMA periods. EMA compliance in the current study was above 80%
633 across the three periods (EMA1 = 82.74%, EMA2 = 83.38%, EMA3 = 80.04%).

634

635 **9. Statistical Analyses Plan**

636 For all tests, a conventional threshold of $\alpha = 0.05$ was used. While opting not to correct
637 for multiple comparisons may permit alpha inflation, we did not want to risk missing any
638 potential therapeutic effects in this treatment study by increasing the likelihood of Type II errors.
639 Therefore, in line with a large body of existing literature, findings that passed the significance
640 level of $\alpha = 0.05$ are presented.

641 **Hypothesis 1a:** To test the reduction in paranoia measured in the lab (active vs. sham
642 stimulation), repeated-measures ANOVAs were performed for self-reported state paranoia
643 measured both before and after the stimulation, while paired-samples t-tests were performed for
644 paranoia-related outcomes measured only after stimulation (i.e., attributional bias and hostility,
645 trust to strangers).

646 **Hypothesis 1b:** Multilevel modeling (MLM) with maximum likelihood robust estimation was

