APPENDIX A: SUPPLEMENTARY MEASURES

MATRICS Consensus Cognitive Battery (MCCB; Stimulation Visit 1). The MCCB (Nuechterlein et al., 2008) was used to capture cognitive function, including processing speed (Trail Making Test: Part A, Animal Naming), working memory (Letter-Number Span), and verbal learning (Hopkin's Verbal Learning Test-Revised). Previous research has found impaired cognitive profiles in patients with schizophrenia (Kern et al., 2011).

Wisconsin Card Sorting Test (WCST; Stimulation Visit 1). The WCST (Berry et al., 2015; Nelson, 1976) was used to assess executive function (e.g., planning, set changing capacity). In this task, 4 stimulus cards and 64 response cards were presented on the computer. Participants were asked to match each response card to one of the stimulus cards according to one of three possible criteria (i.e., color, shape, or number). Immediately following each sort, participants were informed if they were correct or incorrect. After 10 correct sorts, the sorting rule changed, and participants had to discover a new rule. A subsequent string of 10 correct responses triggered another rule change, and this continued until all 64 cards were sorted. The number of categories/criteria achieved, total errors, and perseverative errors (i.e., when the card is sorted according to a category concept that the participant was told was erroneous) were calculated. Previous research has found that more perseverative errors were made by schizophrenia patients with paranoid ideations compared to healthy controls (Berry et al., 2015).

The Fast and Slow Thinking Questionnaire (FaST; Stimulation Visit 1). The FaST (Hardy et al., 2020) contains 10 items measuring fast and slow thinking biases when having paranoid thoughts on a 5-point scale (1 = not at all, 5 = totally; range = 10-50), with higher scores indicating higher proneness for fast or slow thinking. This measure was included because previous research has suggested the involvement of fast and slow thinking biases in paranoia in both clinical and general populations (Garety et al., 2021; Hardy et al., 2020).

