Childhood Trauma Questionnaire (CTQ; Stimulation Visit 1). Given that trauma has previously been associated with paranoia (Freeman et al., 2002; Freeman & Fowler, 2009), we used the CTQ Short Form (Bernstein et al., 2003) to assess childhood trauma and control for it. The CTQ Short Form contains 28 items (e.g., “People in my family said hurtful or insulting things to me”, “I believed that I was physically abused”) on a five-point scale (1 = never true, 5 = very often true). Scores range from 28-140, with higher scores indicating higher level of childhood trauma.

Penn Emotion Recognition Task (ER-40; Stimulation Visit 1 and 2). The ER-40 was used to assess emotion recognition ability (Kohler et al., 2003). Forty color photographs of faces expressing one of 4 basic emotions (happiness, sadness, anger, fear) or a neutral expression were presented to the participants. After viewing each face, they were asked to choose the correct emotion. The dependent variable consists of the accuracy score ranging from 0 to 40, with a higher score indicating higher emotion recognition ability. Impaired ER-40 performance was observed in patients with schizophrenia (Butler et al., 2009), but inconclusive results were reported in studies on individuals with prominent paranoid ideation. Previous research found nonsignificant differences in ER-40 performance between paranoid and non-paranoid patients with schizophrenia (Pinkham, Harvey, et al., 2016); however, individuals with subclinical paranoia showed reduced accuracy in identifying negative emotions compared to individuals with low paranoia (Combs et al., 2013). Some studies also reported that paranoid patients are more likely to misinterpret neutral facial expressions as angry and threatening (Pinkham et al.,

757 2011; Tso et al., 2015).

758 ***Bell Lysaker Emotion Recognition Test (BLERT; Stimulation Visit 1 and 2).*** The
759 BLERT (Bell et al., 1997) measures the ability to recognize seven emotions: happiness, sadness,
760 fear, disgust, surprise, anger, or no emotion. Twenty-one videos (each one lasts ~10 seconds) of
761 a single male actor were presented, which include facial, verbal, paraverbal, and body movement
762 information. Participants were asked to view these segments and identify the emotion shown.
763 The total number of correct identifications was used to reflect performance (range = 0-21), with a
764 higher score indicating better emotion recognition ability. The BLERT has good psychometric

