791 and their ages when they moved (Oishi, 2010).

792 ***Social norm violation task (SNVT; Stimulation Visit 2).*** Recent studies investigating
793 how paranoia affects social decision-making found that paranoia was associated with decreased
794 cooperation and increased punishment towards partners in economic games (Raihani et al., 2021;
795 Raihani & Bell, 2018). In this study, we measured social norm violation perception to test its role
796 in paranoia and aggression. In this social norm violation task (Mu et al., 2015), participants rated
797 the appropriateness of 48 norm-violating behaviors (e.g., "John is talking on his cell phone in the
798 movie theater") on a 7-point scale (1 = strongly inappropriate, 7 = strongly appropriate). All
799 items were reverse-coded, and higher scores reflect being more critical towards the violation.

800 ***The Moralism Scale (MS; Stimulation Visit 2).*** The MS (Janoff-Bulman et al., 2009)

801 was used to further measure the perception of prescriptive (i.e., did not do the good thing, for
802 example, did not help others) and proscriptive (i.e., do the bad thing, for example, cheat or steal)
803 moral violation in the current study. The MS contains 20 scenarios where the character is
804 considering conducting a certain moral (violation) behavior or not (10 items for prescriptive
805 morality and 10 for proscriptive morality). Participants indicated whether the character in each
806 situation should or should not do the behavior on a 9-point scale (1 = feel very strongly he/she
807 should not do, 9 = feel very strongly he/she should). Scores were calculated for prescriptive and
808 proscriptive (will be reverse-coded) morality, respectively, with higher scores indicating a higher
809 weight has been assigned to prescriptive or proscriptive morality.

810 ***Aggression Questionnaire (AQ; Stimulation Visit 2).*** The AQ includes 29 items
811 assessing aggressive behavior and tendencies across 4 dimensions: physical aggression, verbal
812 aggression, anger, and hostility (Buss & Perry, 1992). It is rated on a 5-point scale ranging from
813 1 (extremely uncharacteristic of me) to 5 (extremely characteristic of me), with higher scores
814 indicating higher levels of aggression. In previous research, a significant positive correlation was
815 found between persecutory ideation and aggression reported via AQ in both individuals with
816 SSD and the general community (van Dongen et al., 2011).

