817 ***Novaco Anger Scale and Provocation Inventory (NAS-PI; Stimulation Visit 2).*** The
818 NAS-PI is another self-reported measure examining anger reactions in everyday life (Novaco,
819 2003). The first part of NAS-PI contains 48 items tapping in to 3 dimensions: cognitive, arousal,
820 and behavioral. Participants rated each item along a 3-point scale (1 = never true, 3 = always
821 true), with higher scores indicating higher levels of aggression tendency. The second part
822 contains 25 items depicting provoking situations, and participants rated how angry each of them
823 makes them feel on a 4-point scale (1 = not at all angry, 4 = very angry), with higher scores
824 indicating higher anger disposition. Good psychometric properties have been demonstrated
825 among individuals with psychotic disorders (Novaco, 2003), and previous research has found
826 that NAS-PI was positively associated with the suspiciousness item of PANSS in individuals
827 with psychotic disorders (Bucci et al., 2013)

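### The questionnaires given between stimulation sessions differ by visit and precede the in-lab outcomes, while the SAP has no visit term; this costs some power and, for outcomes measured only after stimulation, adds an avoidable possible source of treatment-by-visit interaction

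*Combined protocol and SAP*

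**What the plan says.** Section 7.3 says that "all measures administered between stimulation sessions can be found in" Appendix A. There, many measures are assigned to one visit.

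- Visit 1 only: "MATRICS Consensus Cognitive Battery (MCCB; Stimulation Visit 1", WCST, FaST, "Childhood Trauma Questionnaire (CTQ; Stimulation Visit 1" and residential mobility history.
- Visit 2 only: "Social norm violation task (SNVT; Stimulation Visit 2", the Moralism Scale, "Aggression Questionnaire (AQ; Stimulation Visit 2" and "Novaco Anger Scale and Provocation Inventory (NAS-PI; Stimulation Visit 2".
- Both visits: SFS (Section 7.3), ER-40, BLERT and the Hinting task.

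The post-stimulation assessments (headed 6.7, after 7.3) then take SSPS, STAI-S, AIHQ, SST, PID-5-HS and the Trustworthiness Task. Section 7.2 uses the SSPS "to examine paranoia levels immediately before and at the conclusion of stimulation within each" visit, and STAI-S is likewise taken before and after; the other four are taken only after. Section 9 plans repeated-measures ANOVA for state paranoia "measured both before and after the stimulation, while paired-samples t-tests were performed for" the outcomes taken only after. No visit, sequence or carry-over term is named. Section 6.2 reports that 26 participants had active stimulation at Visit 1 and 24 at Visit 2.

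**The concern.** Condition order is randomised, but battery content is fixed to visit number. The Visit 2 set is close in subject to some outcomes: the AQ has anger and hostility dimensions, the NAS-PI asks for anger at provoking situations, AIHQ scores anger and blame, and PID-5-HS scores hostility. Answering the Visit 2 set could shift those outcomes at Visit 2, or change how they respond to stimulation.

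A shift common to both conditions adds noise that the planned paired tests leave in. A shift that differs by condition is a treatment-by-visit interaction, which four post-only cell means cannot distinguish from carry-over of the first condition.

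The one-visit measures also feed secondary analyses. Section 7.3 mentions paranoia, social decision-making and aggression, and Appendix A says childhood trauma will be controlled for. Each measure is taken once, after active stimulation for about half the participants and after sham for the rest.

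**Working it through.** **Inputs from the documents.** Order 26/24 (Section 6.2). Target effect 0.25, power 0.80, alpha 0.05, correlation 0.3, N = 46 (Section 4.1). Visit 2-only items: 48 (SNVT) + 20 (Moralism) + 29 (AQ) + 48 + 25 (NAS-PI) = 170, of which 29 + 73 = 102 concern aggression or anger. The documents give no visit means or variances, so every shift, interaction and carry-over size below is an assumption, in SD units.

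**1. The plan's own figure.** The 0.25 is printed as beta but works only as Cohen's f, since beta is 0.20 at power 0.80. For two repeated measures, noncentrality = f²·n·m/(1 − rho) = 0.0625 × 46 × 2/0.7 = 8.21, and power is 0.801. N = 46 reproduces. With the 50 completers, power is 83.4%.

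**2. Plain visit shift S (Visit 2 minus Visit 1).** The active-sham difference has mean T − S in the 26 who had active first and T + S in the 24 who had sham first.
- Bias: S(24 − 26)/50 = −0.04S. For S = 0.5 this is −0.02 SD.
- Variance of a paired difference: 2(1 − 0.3) = 1.4 without a shift. With it, 1.4 + 0.25 × (1 − 0.04²) = 1.65.
- Paired t-test with T = 0.5: noncentrality falls from 0.5 × √(50/1.4) = 2.99 to 0.48 × √(50/1.65) = 2.64, and power from 83.4% to 73.6%. It is 79.1% at S = 0.3 and 53.9% at S = 1.0.
- These figures take the sign of S that works against the active effect. With the other sign at 0.5, noncentrality is 0.52 × √(50/1.65) = 2.86 and power is 80%.
- A simulation that holds the split at exactly 26/24 gives 75% and 82% for the two signs, and 83% for both once a visit term is fitted.

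**3. Interaction and carry-over, post-only outcomes.** Let the effect be d1 at Visit 1 and d2 at Visit 2, and let L be differential carry-over from active stimulation into Visit 2.

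| Sequence | Visit 1 | Visit 2 |
|---|---|---|
| Active first | m + d1 | m + S + L |
| Sham first | m | m + S + d2 |

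- There are five unknowns and four cells (rank 4). The difference in sequence totals is d1 − d2 + L, so only that sum is estimable.
- The visit-adjusted treatment estimate is (d1 + d2)/2 − L/2. An interaction without carry-over leaves the average effect unbiased; carry-over of 0.2 to 0.8 SD shifts it by 0.10 to 0.40 SD.
- The sequence test has SE √(2 × 1.3) × √(1/26 + 1/24) = 0.456. Its power is 7%, 19% and 40% for 0.2, 0.5 and 0.8 SD.
- Each single-visit active-sham estimate compares 26 with 24 people, with SE √(1/26 + 1/24) = 0.283 SD.

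**4. SSPS and STAI-S.** There are eight cells (two sequences, two visits, pre and post). A model with carry-over already present at the Visit 2 pre-score, an additive Visit 2 battery effect and a treatment-by-battery interaction has full rank (7 of 7), because that pre-score precedes the Visit 2 battery. Only carry-over that acts solely on the Visit 2 response stays hidden.

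**The case against.** The strongest reply is that the confounding is not caused by the batteries. Treatment-by-visit is aliased with differential carry-over in every two-period, two-sequence crossover and would remain with identical questionnaires. This stands: the batteries add only a possible cause of interaction.

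Timing weakens a priming account. After the battery come an offered 30-minute break, a 20-minute session and 30 quiet minutes, so at least 20 + 30 = 50 minutes, or 80 with the break, separate it from the outcomes. Nothing in the documents shows that an effect persists that long. The 170 items are not all about anger either; half of the Moralism items concern doing good.

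A reader might infer that any visit-dependent effect is inseparable from carry-over for every outcome. That is too strong: a plain visit shift is estimable, and SSPS and STAI-S have the Visit 2 pre-score. A reader might also infer that the treatment estimate is halved. If stimulation worked fully after one battery and not at all after the other, the pooled estimate would be 26/50 = 0.52 or 24/50 = 0.48 of the effect. Without carry-over, however, that is the correct average over the two visits, and no such pattern is documented.

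On the secondary analyses, Section 7.3 calls them outside the main focus and specifies no model. Several instruments ask about history or everyday habits, which one session may barely move. That limits the importance of the point but does not remove the case for one covariate.

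**Conclusion.** The point holds in a limited form. Battery content is confounded with visit, it precedes the in-lab post-stimulation outcomes, and no visit term is planned. The likely cost is power rather than bias: about 0.04S of bias, and a fall from 83% to between 74% and 80% at an assumed 0.5 SD shift, depending on its sign (true effect 0.5 SD, correlation 0.3). For AIHQ, SST, PID-5-HS and trust, a visit difference in the active-sham effect could reflect battery or carry-over, and the data have little power to show either. The size of any battery interaction is unknown. The documents do not support a claim that the main comparison is invalid, or that the concern reaches the EMA outcomes, which are collected over the following 7 days. SFS is itself a between-session measure, and its place in that battery is not stated.

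**What to change.** **Data already collected** (Section 4.1 reports that recruitment has ended):
- Add a visit (period) term to the in-lab active-sham analyses. It costs one degree of freedom and recovers the lost power.
- Report the active-sham estimate by visit with its confidence interval, noting the low precision (SE about 0.28 SD).
- Compare Visit 2 pre-stimulation SSPS and STAI-S by sequence, as a check on carry-over present at that point.
- State that for the post-only outcomes a visit difference may reflect the battery or carry-over.
- Include that day's condition as a covariate in every secondary analysis that uses a one-visit measure.

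These steps cost a few model terms and some reporting space.

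**A future trial of this design:** keep between-session content the same at both visits (SFS, ER-40, BLERT, Hinting) and place the one-visit instruments after the post-stimulation outcomes. The cost is a longer visit. Those instruments would still follow stimulation, so the condition covariate stays. Moving them to enrollment would avoid that but would put the anger items before the baseline EMA week. Neither change removes the aliasing of interaction with carry-over; it removes one avoidable source of interaction.
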